16 STATISTICAL METHODOLOGY

16.1 SAMPLE SIZE JUSTIFICATION

A total N of 120 patients (60 in each group) will allow, with 80% of power, to rule out a difference between treatment groups greater than 1g/ dl in hemoglobin increase from baseline value to the mean value of the visits between week 8 and 12.

16.2 RANDOMIZATION

All patients will be randomized by an electronic randomization system, stratified by sex and in blocks by site.

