9.1 PATIENT NUMBER

There are plans to recruit 120 patients in total that will be randomized in a 1:1 ratio to receive HEMAX PFS (n = 60) or EPREX/ ERYPO® (n = 60).

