16.6 SAFETY ANALYSIS

The evaluation of safety shall be carried out using the entire population (FAS) of data, making focus on adverse events (AE).

As primary safety objective, the incidence of adverse events and adverse reactions will be evaluated after 12 and 24 weeks of treatment, comparing patients treated with HEMAX PFS versus those treated with EPREX/ ERYPO®.

An AE shall be considered as treatment - emergent adverse event (TEAE), if it presents after the first dose administered of the investigational product or if, preexistent prior to the administration of the first dose, it worsens after the administration of the same.

All TEAEs will be presented summarized through the use of Tables, for each organ class and preferred term to denominate them. The Tables will present the number of patients for which events occurred, and the incidence rate, expressed as a percentage calculated on the number of patients from the entire population included in the safety FAS.

The TEAEs will be presented by causality (relationship with the study drug), intensity (mild, moderate, severe). Treatment - emergent events that are serious and that lead to treatment discontinuation will also be summarized using the preferred term and the class organ system involved.

In addition, and with focus on safety, the following will be discussed:

- Incidence of **thromboembolic events** (myocardial infarction, cerebrovascular accident, deep vein thrombosis and other thromboembolic events).

- Incidence of **hypertension** as TEAE.
- **Blood pressure** values at each visit.
- **Complete baseline laboratory data** and at week 12 and 24 visits,
- **Antibody dosages**, baseline and at weeks 12 and 24.

For safety analysis, descriptive statistics will be performed mainly to evaluate the incidence of adverse events and adverse reactions after 12 and 24 weeks of treatment and x2 test will be performed to compare the incidence of adverse events and adverse reactions of patients treated with HEMAX® PFS versus those treated with EPREX/ERYPO®.

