3.2.4 Statistical Hypotheses

Treatment equivalence will be established if the difference between the two groups excludes a difference between treatment groups greater than 1g/ dl in hemoglobin increase from baseline value to the mean value of the visits between week 8 and 12 with a difference in the mean dose of epoetin alfa in these visits no greater than 20%.

The following equivalence statistical hypotheses is to be tested at a two-sided significance level of 5%:

- H0: Treatment difference in mean Hb during the primary efficacy evaluation period, between treatment arms (HEMAX PFS versus EPREX/ERYPO®), is within ± 1.0 g/dL or less.
- H1: Treatment difference in mean Hb during the primary efficacy evaluation period, between treatment arms (HEMAX PFS versus EPREX/ERYPO®), is greater than ± 1.0 g/dL.

Only when the primary endpoint achieves equivalence, statistical testing will progress to the secondary endpoints according to the stepdown procedure.

4 Study Methods

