4.3 Randomisation and Blinding

All patients were assigned to the corresponding treatment group by an electronic randomization software system, stratified by gender, and in blocks per center. The randomization system was defined in the electronic data collection system.

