The trial starting date was February 15th, 2017 and the first patient was included on February 21st, 2018 and the date in which the last patient reached the primary evaluation criterion was March 23rd, 2021. Since the study started, the recruiting rate was lower than that expected. Many participating centers included one single patient or no one. During the whole study, Biosidus made its best effort to support and accompany the recruitment in the centers. Furthermore, new centers were opened until a total of 16 centers in CABA and Buenos Aires Province were achieved. Besides, amendments to the protocol were performed to include a specialized center in Paraguay.

Since in March 2020, an emergency situation was decreed due to COVID-19 pandemic. On March 20th, 2020, the Argentine National Administration for Drugs, Food, and Medical Devices (ANMAT) issued a set of regulations and recommendations, in a document titled "Regulations and recommendations regarding clinical pharmacology studies during the COVID-19 pandemic", in order to preserve the activities regarding the clinical pharmacology studies, protecting the safety and welfare of the study participants. As a consequence, and according to the clauses, Biosidus S.A. designed a risk mitigation plan (Annex 14.13), that was submitted to the Study Ethics Committees and to ANMAT.

Although the recruiting was not suspended, the health situation determined a reduction in the recruitment ratio. The interim analysis according to the obtained data showed, preliminary, that the results were those expected and allowed the conclusions of this report to be valid enough statistically, though the "n" was lower than that estimated at the beginning.

Considering that the studied population is a population at risk, and that the internal analysis gave consistent results, the recruitment was ended before achieving the 120-patient-target, and finally the study enrolled 43 patients (23 in HEMAX group, and 20 in Eprex/ Erypo® group)..

Thus, the population safety was considered as a priority, and, moreover, the integrity of the results, already collected, were kept.

6 General Considerations

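### Randomisation is stratified by sex, but no planned between-arm analysis includes sex, so reported standard errors are slightly too large and any leftover sex imbalance is not adjusted for (minor)

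*Protocol*

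**What the plan says.** Protocol 13.1 and 16.2 randomise patients "stratified by sex and in blocks by site". SAP 4.3 agrees: "stratified by gender, and in blocks per center". Neither document gives a block size or says whether sex is crossed with site.

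Sex does not reappear in the planned comparisons:

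- **Haemoglobin.** Protocol 16.5 plans an ANCOVA and names the baseline value as its only covariate; the sentence could even be read as attaching that covariate to the within-group analysis. SAP 7 and 8 list no covariates for the between-group model and permit a two-sample t test instead.
- **Responders and transfusions.** Protocol 16.5 and SAP 8.2 name no test and no stratification.
- **Adverse events.** Protocol 16.6 states that a "x2 test will be performed to compare the incidence of adverse events and adverse reactions". SAP 9.1 is mainly descriptive.
- **Baseline.** SAP 7.3 summarises sex as a count and percentage. This is its only stated use.

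SAP 8.1 makes the per-protocol set primary. SAP 5 reports that "new centers were opened until a total of 16 centers", that one centre in Paraguay was added, that many centres contributed one patient or none, and that enrolment stopped at 43 (23 and 20).

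**The concern.** An analysis would normally carry the factor used to stratify randomisation. Stratifying removes part of the between-arm variability due to that factor. A model without the factor leaves its variance in the residual, so the standard error describes a less efficient design than the one used.

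A second issue is specific to this trial. Blocks balance sex only when they fill. With 43 of 120 patients spread over many small centres, some blocks will have stayed incomplete, and per-protocol exclusions can disturb the balance further. With sex in the model, whatever imbalance remains is adjusted for; without it, the imbalance stays in the estimate.

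At stake is a small amount of precision in an equivalence comparison that has already lost most of its planned sample.

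**Working it through.** **The plan's own figure.** Protocol 16.1: "A total N of 120 patients (60 in each group) will allow, with 80% of power, to rule out a difference" "greater than 1g/ dl in hemoglobin increase from baseline value to the mean value of the visits between week 8 and 12". No SD is given, so 120 cannot be reproduced. The SD it implies depends on the formula:

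- two-sided 5%: 1 / [(1.96 + 0.84) × √(2/60)] = 1.96 g/dl
- one-sided 5%: 2.20
- two one-sided tests with true difference zero: 1.86 (5% per side) or 1.68 (2.5% per side)

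The work below assumes a residual SD of 1.5 g/dl.

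**How much variance sex could explain.** Assume half the patients are women and the sexes differ by d in haemoglobin change. The share explained is R² = 0.25d² / (1.5² + 0.25d²), and leaving sex out widens the interval by 1/√(1 − R²).

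- d = 0: R² = 0, no widening
- d = 0.3: 0.0225/2.2725 = 1.0%, widening 0.5%
- d = 0.5: 0.0625/2.3125 = 2.7%, widening 1.4%
- d = 0.8: 0.16/2.41 = 6.6%, widening 3.5%
- d = 1.0: 0.25/2.5 = 10%, widening 5.4%

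**Simulation.** 4,000 runs per setting; no treatment difference; SD 1.5; half women; 17 sites of unequal size; blocks of 4; models with and without sex, and no baseline covariate. The SD, sex share, site sizes and block size are assumptions.

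| N | Strata | d (g/dl) | True SD of unadjusted estimate | Reported SE, unadjusted | Reported SE, sex in model |
|---|---|---|---|---|---|
| 120 | sex | 0 | 0.274 | 0.273 | 0.273 |
| 120 | sex | 0.5 | 0.273 | 0.277 | 0.273 |
| 120 | sex | 1.0 | 0.271 | 0.288 | 0.273 |
| 43 | sex | 0 | 0.465 | 0.454 | 0.454 |
| 43 | sex | 0.5 | 0.451 | 0.461 | 0.455 |
| 43 | sex | 1.0 | 0.457 | 0.480 | 0.454 |
| 43 | sex within site | 1.0 | 0.476 | 0.482 | 0.460 |

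Simulation error on each true SD is about 1/√8000 = 1.1%.

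- *Reported SE.* With sex-only strata, adding sex cuts it by about 5% at d = 1.0, about 1% at d = 0.5 and nothing at d = 0. This agrees with the formula.
- *True precision.* It hardly changes when sex is added: at d = 1.0 with sex-only strata, from 0.271 to 0.271 (N = 120) and from 0.457 to 0.456 (N = 43). The design has already secured it. With no stratification, the unadjusted true SD at d = 1.0 would be 0.285 and 0.481.
- *Rejection rate at nominal two-sided 5%* (d = 1.0, sex-only strata). Unadjusted, 3.6% (N = 120) and 4.0% (N = 43); with sex, 4.5% and 5.1%. Simulation error is √(0.05 × 0.95/4000) = 0.34 points.

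**Residual imbalance at N = 43.** The 95th percentile of the absolute difference in the proportion of women is 7 points with sex-only strata, 20 with sex within site and 30 unstratified. At d = 0.5 to 1.0, a 20-point imbalance moves the estimate by 0.10 to 0.20 g/dl, and a 7-point one by 0.035 to 0.07. Across repeated randomisations this is variance. The SD of the imbalance under sex-within-site strata is 0.098, so at d = 1.0 a standard error of 0.46 becomes √(0.46² + 0.098²) = 0.470, about 2% larger. The mean unadjusted estimate stayed within 0.02 g/dl of zero in every setting. Per-protocol exclusions were not simulated.

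**Scale against the margin.** With 23 and 20 patients, SE = 1.5 × √(1/23 + 1/20) = 0.459. The 95% half-width is 2.02 × 0.459 = 0.93 g/dl with sex in the model. Without it, the half-width is about 0.94 (d = 0.5) or 0.98 (d = 1.0), against a margin of 1 g/dl.

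**The case against.** The strongest reply is that the loss is small, in the safe direction, and rests on a sex effect the documents never state. At zero effect there is nothing to gain. That stands, and it sets the severity.

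It can also be said that the plan does not choose to pool the sexes: it leaves covariates and most tests unspecified, and the wording that settles ANCOVA versus t test would settle this too. That stands in part. One amended sentence closes both gaps, but the baseline value is the only covariate named anywhere, and a t test cannot carry sex at all.

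A reader might infer more than the documents support:

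- *That stratification buys no precision.* It does; the true SD falls. Only the reported standard error misses the gain.
- *That sex balance is close to chance.* The usual formula, √[0.25 × (1/23 + 1/20)] = 15 points, describes no stratification at all. The simulated 95th percentiles are 7 or 20 points against 30. Counting 17 × 2 = 34 cells presumes that sex is crossed with site, which is not stated, and includes centres that enrolled no one.
- *That every binary and safety comparison needs stratifying.* No benefit has been shown for transfusions or adverse events in 43 patients.

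**Conclusion.** The point holds as a minor one. The trial stratifies by sex and plans no between-arm analysis that uses it. The consequence is a reported standard error too large by roughly 0 to 5% for an assumed sex effect of 0 to 1 g/dl (about 1% at 0.5 g/dl), with sex imbalance from unfilled blocks and exclusions left unadjusted. The two effects trade off: the better the blocks worked, the more conservative the unadjusted test; the worse they worked, the more imbalance remains to adjust for.

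A reader might infer a biased result or a raised risk of false equivalence. Neither follows. Imbalance left by randomisation averages out. An interval that is too wide makes equivalence harder to show, and under an additive sex effect this is so at any true difference, including one at the margin. Per-protocol exclusions related to treatment and outcome are a different problem, which adjusting for sex would not cure.

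The sizes rest on the assumed SD of 1.5 g/dl, half women, 17 sites and blocks of 4. A larger SD makes the same sex effect matter less.

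**What to change.** In SAP 7, 8 and 8.1, state that the between-arm haemoglobin comparison is an ANCOVA with treatment, baseline haemoglobin and sex, and remove the t-test option for the primary comparison. State that site is left out because the centres are too sparse to support a site term, so that the omission is a recorded decision.

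A sex-stratified Mantel-Haenszel risk difference with its confidence interval is optional for the responder percentage, where SAP 8.2 names no method. For transfusions and adverse events the gain is negligible at this size and no change is needed.

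The cost is one degree of freedom; sex is already collected. Because SAP 5 reports the final enrolment and the interim findings, and the trial is open-label, the SAP should disclose that the covariate was added after interim results were known.

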16.3 PATIENT DATA ANALYSIS GROUPS

The data analysis groups or populations are listed below.

16.3.1 Full Analysis Set (FAS)

The full data analysis group will consist of all patients enrolled in this study that have been randomized and who have received at least one dose of the study medication.

16.3.2 Per Protocol (PP) analysis group

The per protocol data analysis group will consist of all patients enrolled in this study who have received at least one dose of the study medication, who have completed at least one follow - up visit and that do not have major protocol violations.

16.4 DATABASE ANALYSIS

There will be two formal database analyses.

- A first analysis will be performed after the last study patient completes the week 12 visit and the database is clean. This analysis will produce all the efficacy and safety results at week 12.
- A second analysis will be performed after the last study patient completes the week 24 visit and the database is clean. This analysis will produce all the safety results, including immunogenicity, at week 24.

16.5 EFFICACY ANALYSIS

The efficacy analysis will be performed for both FAS and PP populations. Descriptive statistics and inferential statistics will be performed through intergroup analysis (ANCOVA covariance analysis)-comparing each treatment group (patients treated with HEMAX PFS versus those treated with EPREX/ERYPO®) and an additional intragroup analysis analyzing the variations in hemoglobin (increase from baseline to the average of the visits between weeks 8 and 12) adjusted for the baseline value, using a significance level of 5%. Statistical analysis will be performed with SPSS software or equivalent.

The following parameters will be evaluated for treatment efficacy, according to the objectives defined by the protocol.

The **primary efficacy assessment** will be carried out through the levels of hemoglobin increase from baseline value to the mean value of the visits between week 8 and 12, comparing patients treated with HEMAX PFS versus those treated with EPREX/ERYPO®.

Additionally, **treatment equivalence** will be established if the difference between the two groups excludes a difference between treatment groups greater than 1g/ dl in hemoglobin increase from baseline value to the mean value of the visits between week 8 and 12 with a difference in the mean dose of epoetin alfa in these visits no greater than 20%.

The **secondary efficacy assessment** will be carried out through the evaluation of the following objectives:

- Percentage of responder patients (increase of Hb \geq 1g/ dl) after 12 weeks of treatment, comparing patients treated with HEMAX PFS versus those treated with EPREX/ERYPO®.

- Percentage of transfusion requirement after 12 weeks of treatment, comparing patients treated with HEMAX PFS versus those treated with EPREX/ ERYPO®.
- Intragroup efficacy (HEMAX PFS and EPREX/ ERYPO®) of treatment with Epoetin Alfa through increased levels of hemoglobin from baseline in each one of the intermediate visits until the week 12 visit.
- Evaluate the intragroup efficacy (HEMAX PFS and EPREX/ ERYPO®) of the change from the twice - a - week dosing during the titration phase to a weekly dosing during the maintenance phase through the variation of the hemoglobin levels from week 12 to the weeks 16, 20 and 24.

For **missing hemoglobin data**, the last observation carried forward method will be used.

In an exploratory way, the basal level of hepcidin at 12 and 24 weeks will be evaluated in relation to the response to treatment in order to observe the relationship between the basal levels of hepcidin with the fall in filtrate and the hemoglobin level. We will also observe the response of hepcidin levels to treatment with erythropoietin and finally we will see if there is any type of association between hepcidin levels and the subgroup of patients who do not respond to erythropoietin.

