6.2 Analysis Populations

6.2.1 Per Protocol Population

- All subjects who received any study drug and who completed at least week 12 follow up visit to evaluate primary efficacy endpoint and who did not substantially deviate from the protocol.

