6.3 Missing Data

Para los datos faltantes de hemoglobina se utilizará el método de la última observación llevada hacia adelante (LOCF).

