8.2 Secondary Efficacy Analyses

- Percentage of responder patients (increase of Hb \geq 1g/ dl) after 12 weeks of treatment, comparing patients treated with HEMAX PFS versus those treated with EPREX/ ERYPO®.
- Percentage of transfusion requirement after 12 weeks of treatment, comparing patients treated with HEMAX PFS versus those treated with EPREX/ ERYPO®.
- Intragroup efficacy (HEMAX PFS and EPREX/ ERYPO®) of treatment with Epoetin Alfa through increased levels of hemoglobin from baseline in each one of the intermediate visits until the week 12 visit.
- Evaluate the intragroup efficacy (HEMAX PFS and EPREX/ ERYPO®) of the change from the twice - a - week dosing during the titration phase to a weekly dosing during the maintenance phase through the variation of the hemoglobin levels from week 12 to the weeks 16, 20 and 24.

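### Unlimited LOCF for missing Hb can bias the weeks 8–12 comparison in either direction and, read literally, enters zero change at weeks 16–24 for patients withdrawn by rule at week 12

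*Protocol*

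**What the plan says.** Protocol 16.5 gives one rule for missing Hb: "the last observation carried forward method will be used". SAP 6.3 consists of a single Spanish sentence to the same effect: "se utilizará el método de la última observación llevada hacia adelante (LOCF". No restriction and no sensitivity analysis is stated in either place.

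The primary endpoint is "levels of hemoglobin increase from baseline value to the mean value of the visits between week 8 and 12". Equivalence is claimed if a difference above 1 g/dl is excluded, together with a condition on mean dose.

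The analysis sets differ between the documents:
- Protocol 16.5 requires efficacy in both FAS and PP. FAS needs one dose (16.3.1). The protocol's PP set needs one follow-up visit and no major violation (16.3.2).
- SAP 8.1 runs the primary analysis in PP only, and SAP 6.2.1 restricts PP to patients "who completed at least week 12 follow up visit to evaluate primary efficacy endpoint". SAP 7.2 lists a missing evaluable week 12 Hb among the deviations that could exclude a patient.

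Protocol 9.4 and 10.1 withdraw patients whose Hb has not risen by 1 g/dl at week 12; only the others enter maintenance. The dosing-switch endpoint is assessed "through the variation of the hemoglobin levels from week 12 to the weeks 16, 20 and 24" (SAP 8.2; the protocol is equivalent). Neither document names the patients who belong in that analysis.

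**The concern.** Hb is meant to be rising during titration: protocol 4.3 places clinically significant increases at 2 to 6 weeks, and protocol 10.1 allows dose increases at weeks 4 and 8. An Hb from week 2, 4 or 6 is therefore a poor stand-in for the weeks 8–12 mean. Early withdrawal is also built in, since transfused patients leave the study (protocol 11.3). In an equivalence trial, any bias that pulls the arms together helps the claim. A bias that depends on who leaves, and when, is not controlled in either direction.

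The maintenance endpoint has a separate problem. A week 12 non-responder completed week 12, so he or she can belong to the SAP's PP set but has no later visits. Carrying week 12 forward makes the change from week 12 exactly zero, for a patient who never switched to weekly dosing. In the FAS the same happens to anyone who left before week 12.

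**Working it through.** **Inputs.** From the documents: margin 1 g/dl, 60 per arm and 80% power (protocol 16.1); 43 enrolled, 23 and 20 (SAP section 5); the SAP's "equivalence statistical hypotheses is to be tested at a two-sided significance level of 5" per cent, read here as a 95% interval inside ±1 g/dl (2.5% per side). Not in the documents, so assumed: SD of the Hb change, dropout share d, time of last Hb, and shape of the rise.

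**1. The plan's own figure.** The statement "A total N of 120 patients (60 in each group) will allow, with 80% of power" comes with no SD, so it cannot be reproduced. Solving backwards at true difference 0: SD = 1 × √(60/2) / (1.960 + 1.282) = 5.477/3.242 = 1.69. A 90% interval gives 5.477/(1.645 + 1.282) = 1.87. The check uses 1.69 and, as an alternative, 1.0.

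**2. What LOCF keeps, FAS or protocol PP.** Let Hb change be linear in week. The weeks 8, 10 and 12 mean then corresponds to week 10. A patient last measured at week 0 (baseline), 2, 4, 6, 8 or 10 keeps 0, 20, 40, 60, 80 or 93% of the true change. If these times are equally likely the mean kept is m = 0.489. With the same d in both arms, expected difference = true difference × [1 − d(1 − m)]. For a true 1.0 g/dl:
- d = 10%: 1 − 0.1 × 0.511 = 0.95
- d = 20%: 0.90
- d = 30%: 0.85

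A saturating rise (time constant 5 weeks, m = 0.626) gives 0.96, 0.93 and 0.89.

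**3. False equivalence at a true 1.0 g/dl.** Simulation, 20,000 replicates, linear rise, equal dropout, 95% interval rule:

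| Arms, SD | No dropout | 10% | 20% | 30% |
|---|---|---|---|---|
| 60/60, 1.69 | 2.4% | 3.9% | 5.5% | 8.0% |
| 60/60, 1.0 | 2.6% | 4.6% | 8.3% | 13.8% |
| 23/20, 1.0 | 2.4% | 3.7% | 5.5% | 8.1% |
| 23/20, 1.69 | 0.6% | 1.2% | 1.9% | 3.1% |

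In the last row the interval rarely fits inside ±1, so the error starts below 2.5%.

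**4. Unequal dropout.** Let the worse arm rise by r₁ with dropout d₁, and the better arm by r₂ with dropout d₂. The expected difference is r₁[1 − d₁(1 − m)] − r₂[1 − d₂(1 − m)]. It moves away from zero when d₁r₁ > d₂r₂.
- Rises 1.0 and 1.5 (true −0.5), dropout 20% and 10%: 0.898 − 1.423 = −0.53. At 30% and 10%: 0.847 − 1.423 = −0.58.
- Rises 1.5 and 1.5 (true 0), dropout 20% and 10%: −0.08. At 30% and 10%: −0.15.
- Rises 0.5 and 1.5 (true −1.0), dropout 20% and 10%: −0.97, still slightly toward zero, because 0.20 × 0.5 < 0.10 × 1.5.

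**5. The SAP's primary PP analysis.** Week 12 is observed, so only weeks 8 and 10 can be filled. One of them missing: (6 + 10 + 12)/3 or (8 + 8 + 12)/3 = 9.33, which keeps 93.3%. Both missing: (6 + 6 + 12)/3 = 8, which keeps 80%. If this affects 10/20/30% of patients, the shrinkage is 0.7/1.3/2.0% (one missing) or 2/4/6% (both missing).

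**6. Weeks 16–24.** Suppose maintained patients truly change by −0.5 g/dl (SD 1.0), and a share q is carried forward as zero. The mean becomes −0.5(1 − q): −0.45, −0.40, −0.35 and −0.30 for q = 10, 20, 30 and 40%. As an illustration with all 43 patients pooled and about 20% carried forward (34 observed, q = 9/43 = 0.209): the SE in observed patients is 1/√34 = 0.171. With imputed zeros it is √{[0.791 × 1 + 0.209 × 0.791 × 0.25]/43} = 0.139. The 95% interval moves from (−0.84, −0.16) to (−0.67, −0.12). The planned analysis is within arm, so actual SEs would be larger, but the distortion is of the same kind.

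**The case against.** A reader might infer that LOCF always pulls this trial toward equivalence. The documents do not support that. The pull needs similar dropout in both arms and a difference still widening up to week 12. Transfusion withdrawal is related to response and may be commoner in a worse arm; step 4 shows that this can enlarge the difference. The titration rules (increases for low response, interruption at 11.5 g/dl) could also bring the arms together later, in which case an early value would overstate the difference. This objection stands, and the direction must be left open.

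A reader might also infer that the SAP's primary result is seriously distorted. It is not, on these figures: requiring week 12 leaves LOCF little to fill, and the early-dropout scenario behind step 3 does not apply to that set. What survives is the protocol's FAS requirement, its looser PP set, and the maintenance endpoint.

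Third, weeks 16–24 could be regarded as not due, rather than missing, for patients who never entered maintenance. That is a sensible reading, but neither document states it. The zeros follow from the literal text, and the text should settle the matter.

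Finally, the significance level affects the error figures. With 5% per side they start at 5% instead of 2.5% and are correspondingly higher; the SAP's wording fits the 2.5% reading better.

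**Conclusion.** The point holds in this limited form. The LOCF rule has no boundary in either document. Where early leavers are retained, it replaces a weeks 8–12 value with one from the rising phase, and the arm difference can be biased either way. With equal dropout of 10–30% and a linear rise, a true 1.0 g/dl difference is expected to read 0.95 to 0.85. False equivalence then rises from about 2.5% to about 4–8% (60/60 with SD 1.69, or 23/20 with SD 1.0); the other settings checked reach 13.8% and 3.1% at 30% dropout. In the SAP's primary PP analysis the effect is about 1–6% shrinkage. At weeks 16–24 the literal rule would report a 0.5 g/dl fall as 0.40 to 0.30 with 20–40% carried forward, and with an SE that is too small.

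Every magnitude rests on an assumed SD, dropout pattern and trajectory. The absence of any limit on LOCF and the undefined maintenance set do not depend on those assumptions. This should be changed, but it does not by itself invalidate the primary comparison.

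**What to change.** - In protocol 16.5 and SAP 6.3, replace LOCF as the main method with a mixed model for repeated measures on Hb change at weeks 2–12, with terms for treatment, visit, treatment by visit, baseline Hb and sex. Take the arm difference averaged over weeks 8, 10 and 12.
- State that the model assumes data are missing at random. Add a sensitivity analysis that shifts missing values toward non-equivalence, in each direction because the claim has two limits. Keep LOCF as a further sensitivity analysis.
- Define a set of patients who entered maintenance, and limit the week 12 to 16, 20 and 24 analysis to it, using the same kind of model.
- SAP section 5 reports that interim results had been seen when recruitment ended. Date and document the change as made after that look, and report the LOCF and model estimates side by side.

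The cost is wording and standard SPSS or R code; no new data are needed. The interval may be slightly wider than under LOCF. With 43 patients, an unstructured covariance over six visits has 6 × 7/2 = 21 parameters, so a fallback structure should be named in advance.
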